6.2.5 Tracking of Doses

Since the immediate pre- and post-operative periods are busy and nurses frequently have numerous tasks to perform, it is important to measure how many CN-105 (or placebo) doses are given as ordered to assess feasibility of q6 h dosing. We will track whether each CN-105 (or placebo) dose is given within +/-90 min of the scheduled administration time per nursing records.

We will report the observed rate of doses administered within the required time window and the 95% confidence interval. Each dose will be counted as an independent observation. The total number of doses correctly administered (i.e. within 90 min of the scheduled administration time) divided by the number of prescribed doses will define our dosing feasibility rate. Post-hoc feasibility analysis will be performed both among all study patients (including those receiving placebo), and specifically among CN-105 drug patients only, as well as by dose level to determine if drug dose level affects feasibility.

6.3 Study Agent Accountability Procedures

For each participant dose, details of study agent preparation and administration, i.e., time, date, dose level, volume, infusion time, etc., will be recorded in the source documents.

Upon receipt of CN-105 shipments, the pharmacist/designee will verify the condition of the vials and document per instructions in the Manual of Operational Procedures.

All used study agent vials, syringes, infusion sets, etc., will be kept in a secure location. After accountability is complete, used supplies may be discarded according to the site's normal procedures. All study vials (used/unused) remaining at the completion of the study will either be returned to the sponsor/designee or will be destroyed at the site. In case of the latter, the site will

7 TRIAL PROCEDURES AND SCHEDULE

7.1 Trial-Specific Procedures

7.1.1 *Initial Lumbar Puncture and Blood Draw*

An LP will be performed prior to surgery (between the time of consent and the time of scheduled anesthesia/surgery start), with a standard spinal anesthesia kit containing a 25 gauge pencil-point needle (or other appropriate spinal needle per Good Clinical Practice) under strictly sterile conditions. The patient's back will be sprayed with benzocaine numbing spray and we will wait approximately 10 minutes for analgesic relief prior to performing the lumbar puncture. This preoperative LP will be performed by an anesthesiology attending physician or senior anesthesiology resident or fellow under attending supervision, or a nurse practitioner or physician assistant under appropriate supervision.

The LP will be performed using a standard spinal anesthesia kit per the manufacturer's directions under sterile conditions at the L4–5 spinal level or the next interspace above or below this level, depending on which interspace appears larger by palpation. A curvilinear ultrasound probe will be used when necessary to help visualize the interspace. An initial 1 ml of CSF will be discarded (to reduce blood contamination of the CSF) before collecting a study sample of up to 20 ml of CSF. Blood (up to 10 mL) will be collected via sterile venipuncture, from an arterial line, or by the IV line placed before surgery. To assess their level of pain following the lumbar puncture procedure, subjects will be asked to answer the following question: How much did the lumbar puncture hurt (on a scale of 0-10, where 0 is no pain at all and 10 is the worst pain imaginable?)

LP vital signs will be collected and recorded by the study team before and after the LP if performed on outpatient basis (between the time of consent and surgery day).

If the LP is performed while inpatient (i.e. on the day of surgery, or at 24 hrs after surgery), the study team will not collect and record pre and post LP vital signs, as these will already be recorded in the patient's hospital electronic medical record per standard of care.

7.1.2 *Postoperative Lumbar Puncture and Blood Draws*

LPs at 24 hours and at 6 weeks +/- 3 weeks after the start of anesthesia/surgery will be performed by an anesthesiology attending physician or senior anesthesiology resident or fellow under attending supervision, or a nurse practitioner or physician assistant under appropriate supervision. To assess their level of pain following each lumbar puncture procedure, subjects will be asked to answer the following question: How much did the lumbar puncture hurt (on a scale of 0-10, where 0 is no pain at all and 10 is the worst pain imaginable?)

If the participant is hospitalized overnight after the surgery, the 24-hour postoperative LP may be performed in the participant's hospital room, in the preoperative holding area, or in other appropriate space for performing a sterile neuraxial procedure per Good Clinical Practice (GCP) guidelines. If the participant is unexpectedly discharged after surgery on the same day and does not spend the first night in the hospital, the patient will be asked to return for these procedures, and then the 24-hour postoperative LP will be performed in the same location as the 6 week +/- 3 weeks postoperative LPs are performed or in another safe location for performing sterile neuraxial anesthetic procedures per GCP guidelines. As for the preoperative LP, an initial 1 ml of CSF will be

discarded (to reduce blood contamination of the CSF) before collecting up to a 20ml CSF sample for the study.

The 6 week +/- 3 week postoperative LPs will also be performed in the preoperative or postoperative holding area, or in other clinical research space of the Duke Anesthesiology department that is appropriately outfitted for human subject procedures (i.e. presence of medical gases, suction, resuscitation equipment. As with the preop and 24 hr postop LPs, an initial 1 ml of CSF will be discarded (to reduce blood contamination of the CSF) before collecting up to a 20ml CSF sample for the study.

The 24 hr and 6 week +/- 3 week postoperative LP vital signs will be collected and recorded by the study team before and after the LP if performed on outpatient basis. If the LP is performed while the patient is an inpatient, the study team will not collect and record vital signs, as these will already be obtained by the patient's clinical care team and recorded in the patient's hospital record per standard of care.

The LP will then be performed at the L4-5 interspace or the interspace above or below this level, depending on which space feels more open by palpation and/or appears more open by ultrasound visualization. The LP will be performed using a spinal anesthesia kit per the manufacturer's directions under sterile conditions. The participant may be continuously monitored for 15 minutes or longer if deemed necessary.

Blood will be drawn by sterile venipuncture, or from an arterial or an IV line if already in place, at the same time as the lumbar punctures.

7.1.3 Neurocognitive Testing, Delirium Testing, and Other Assessments

Neurocognitive testing and assessments may be performed remotely via teleconference or may be performed in-person in one of the study testing offices located in Duke South or other appropriate location preoperatively (baseline) and/or at 6 weeks +/- 3 weeks after surgery. They will also occur for any patients who have a 1 year post-operative study visit. Tests from the following standardized tests and assessments list will be utilized, which have equivalent alternate forms (to minimize test-retest practice effects) and have English, French and Spanish language versions:

- a. Hopkins Verbal Learning Test, Revised (HVLT-R) - an auditory-verbal word-list task used to assess learning, short-term recall, long-term recall and recognition memory that is co-normed with the BVMT-R (see immediately below).
- b. Brief Visuospatial Memory Test, Revised (BVMT-R) – a visual measure of constructional praxis, spatial/figure learning, short-term recall, long-term recall and recognition memory that is co-normed with the HVLT-R (see immediately above).
- c. Digit Span subtest from the Wechsler Adult Intelligence Scale, 3rd Revision (WAIS-III) – a test of immediate auditory-verbal recall and complex attention (i.e., working memory).
- d. Digit Symbol Coding subtest from the Wechsler Adult Intelligence Scale, 3rd Revision (WAIS-III) - a matching-to-sample visual scanning and visuomotor production task.
- e. Trail Making Test (TMT), Parts A & B – a test of simple visuomotor scanning and complex sequencing and set-switching executive demands.
- f. Controlled Oral Word Association Test (COWAT) – a test of lexical verbal fluency and information retrieval efficiency.
- g. Grooved Pegboard Test – a timed test of bilateral manual dexterity and motor speed.
- h. Wechsler Test of Adult Reading (WTAR) – a non-phonemic reading test used to assess crystallized pronunciation knowledge; a reliable estimate of premorbid intellectual

functioning.

- i. MoCA: used to screen for cognitive impairment.
- j. STOP-Bang brief questionnaire: to assess sleep apnea risk during one of the participants' trial visits.
- k. Visual analogue scale (VAS) pain assessment at each trial visit (preoperative, 6 weeks +/- 3 weeks postop).

Other assessments performed at both the preoperative and 6 week (+/- 3 week) postop visits may include:

- a. List of medications participants are currently taking at each trial visit.
- b. Timed up and Go task/test, Romberg assessment, and falls assessments. In particular, patients will undergo a brief falls risk assessment questionnaire, which contains questions from the Elderly Falls Screening test (Cwikel J et al, Disabil Rehab, 1998) and the Fall Risk Screening test (Tromp et al, J Clin Epidemiology, 2001), and questions about whether they have fallen recently.

Relevant tests listed above may be recorded using a digital voice recorder for quality assurance purposes. Quality assurance activities will include reviewing of testing audio files, generating performance review documents, and providing feedback on accuracy and completeness. There is no risk to the trial participants since participant identifiers will not be provided. Trial participants will not be identified by name on the recording. Only the trial number, test date, and initials of the tester will be provided on the digital file label. The link between trial number and participant identifiers will be maintained. These files will be stored on locked computers within locked offices to which only authorized research personnel will have access. These files will be destroyed after the primary outcome analysis of this research trial is complete.

Delirium Testing will be performed twice daily starting on the day of surgery until postoperative day 5 or hospital discharge (whichever occurs first), as well as at the baseline study visit and the 6 week +/- 3 weeks postoperative study visit, as well as the 1 year visit that some patients may have, using the CAM-ICU instrument in intubated patients (Ely EW et al, 2001) and the 3D-CAM instrument in non-intubated patients (Marcantonio E et al, 2014), based on the enhanced sensitivity of these instruments in these respective patient populations (Kuczmarska A et al, 2016). On the day of surgery, delirium testing will be performed once while the patient is in the post-anesthesia care unit (PACU) after surgery and once later in the afternoon or early evening on the day of surgery, unless the PACU delirium assessment is performed after 4:00 PM. In that case, no additional afternoon/evening testing assessment will be performed on that day. If the surgery ends late and if the PACU delirium assessment cannot be performed before 7:00 PM, then no delirium assessments will be performed on the day of surgery. Inter-rater reliability for these assessments will be assessed as previously described (Marcantonio E et al, 2014).

7.1.4 *Quality of Life Assessment*

Our approach to measuring QOL for this trial involves the use of a battery of well-tested and well-validated instruments that together cover the relevant domains of interest. For this trial, we propose to use an assessment instrument that the Randt group developed, the SF-36 generic QOL instrument, from their longer instruments used in the Health Insurance Experiment and in the Medical Outcomes Study, as well as functional status measures (the Duke Activity Status Index [DASI]); psychological measures, including depression (the Center for Epidemiological Studies- Depression [CES-D]), the State Trait Anxiety Inventory [STAI], and the Hopkins Symptom Checklist [HSCL] (SCL-90); and

social/role functioning (including employment status).

Participants will complete these questionnaires during the baseline trial visit after completing all consent paperwork and again at the 6 week +/- 3 weeks postoperative visit. Any participant who is unable to complete this questionnaire at either trial visit will be given an e-copy or a paper copy of the questionnaire to fill out at home and to mail back to our study team at his or her convenience (in the case of paper questionnaires). Mail in questionnaires will be accepted from patients as long as they are completed by the patient within +/- 3 weeks of the preoperative study visit and before the surgery, or if they are completed within +/- 3 weeks of the 6 week +/- 3 week postoperative study visit.

7.1.5 *Electroencephalographic Recording*

Scalp recordings of electrical activity produced by the brain (EEGs) will be obtained for 3-60 minutes before the start of anesthesia, as well as during and right after anesthesia and surgery. The EEG will be recorded from 32 electrodes embedded in an elastic scalp electrocap, using a state-of-the-art, battery-operated, portable EEG system (Live-amps, Brain Vision LLC, Morrisville, NC). If necessary due to time constraints or other considerations, the study team may also use a BIS electrode strip to monitor the patient's brain waves instead of the full 32 channel EEG cap setup. The electroencephalographic data will be analyzed to determine the effect of CN-105 on EEG correlates of postoperative cognitive function and post-operative delirium, as well as to identify possible novel pre- and intraoperative EEG correlates of POCD, delirium, and/or neuroinflammation (with the latter as measured by CSF inflammatory cytokine levels at 24 hours after anesthesia and surgery). In the event that sufficient personnel or equipment are unavailable, or in the event that two MARBLE patients are having surgery at the same time, or in the event that there is insufficient time to place the EEG sensor on that patient's head before the start of surgery, the study team may not record EEG from all patients or at all points before, during, and just after surgery/anesthesia.

In addition to passive EEG recordings, patients may also undergo auditory event related potential testing during EEG recording in which brief sounds will be administered via earphones during the pre-operative and/or intra-operative EEG recordings, when the pre-op and surgical workflow allows and when study personnel are available. The volume of these brief intermittently played sounds would be well within the range of normal daily exposures, i.e., <= 80 dB, a level that would be safe for even a full day of continuous exposure (MRC Institute of Hearing Research, 1996), which is much more than is proposed here. Patients may further undergo brief audiometric screening in which sounds are delivered via headphones to ensure that they are able to hear the presented sounds at a volume of 80 dB or less without auditory assist devices (i.e., without hearing aids, cochlear implants, or BAHA devices). This would not require any additional visits. EEG responses to auditory event-related potentials have been associated with neurocognitive reserve previously (Speer and Soldan, 2015). Collecting this data may increase the team's ability to identify EEG-based biomarkers of perioperative neurocognitive resilience.

7.2 Standard-of-Care Trial Procedures

7.2.1 *Anesthetic Treatment*

All participants will receive either general anesthesia or sedation (i.e. monitored anesthesia care); patients may also receive regional or neuraxial nerve blocks as adjuncts.

The duration of anesthetic exposure shall be recorded for each participant, and intraoperative anesthetic medication administration and physiologic monitoring data will be extracted from the electronic anesthetic records for post-hoc analyses.

7.3 Laboratory Procedures/Evaluations

7.3.1 Clinical Laboratory Evaluations

A basic metabolic panel (i.e. Na⁺, K⁺, Cl⁻, CO₂, BUN, Cr and glucose) and a complete blood count (with differential) will be measured at three time points: within 2 weeks before anesthesia and surgery (and before the first dose of CN-105), 1 day after the start of anesthesia/surgery (i.e., after ~4 doses of CN-105), and at the 6 week +/- 3 weeks postoperative study visit.

7.3.2 Other Assays or Procedures

We will measure CN-105 levels in both the serum and CSF at the 24-hour postoperative time point. This will help us determine how the CN-105 doses administered to patients in this study translate into serum drug concentrations, and will help us determine the extent of CN-105 penetration in the human CNS (as assayed in the CSF). We note that we do not plan to perform these measurements at the preoperative time point (as there should be no CN-105 in the serum or blood before the first dose is administered), or at the 6 week +/- 3 weeks postoperative study appointment (as the last CN-105 dose will be given no later than on postoperative day 3, and thus CN-105 levels would be expected to be undetectable ~6 weeks later).

We will perform serum and CSF CN-105 measurements together with our colleagues at MPI research (Mattawan, MI; now part of Charles River Laboratories), with whom AegisCN has previously performed these measurements. In brief, CN-105 will be detected via a previously validated high-performance liquid chromatography-tandem mass spectrometry assay (LC-MS/MS). The liquid chromatography system uses an ACE 3 C8 column, 2.1 x 50 mm (3 µm particle size) with an isocratic flow consisting of water/acetonitrile/heptafluorobutyric acid (76/24/0.05, v/v/v) at a flow rate of 200 µL/minute (Agilent 1200 Binary Pump) and a post column infusion consisting of isopropanol/acetic acid (100/1, v/v) at a flow rate of 800 µL/minute (Agilent 1100 LC Quaternary Pump). The analyte and internal standard (acebutolol hydrochloride) are detected using a SCIEX API 5000 triple quadrupole LC-MS/MS system equipped with an ESI (TurboIonSpray[®]) ionization source operated in the positive ion mode. Multiple reaction monitoring transitions of the respective [M+H]⁺ ions are used to monitor CN-105 and acebutolol hydrochloride.

7.3.3 Specimen Preparation, Handling, and Storage

Blood samples will be used for genotyping and metabolic/inflammatory marker assays. Whole-blood specimens (10 mL total volume) will be collected sometime between the patient being consented and scheduled anesthesia/surgery start time, 24 +/- 2 hours later, and 6 weeks +/- 3 weeks later.

Whole-blood specimens will be collected with EDTA as the anticoagulant, obtained either from an arterial or IV catheter or from sterile venipuncture.

Cerebrospinal fluid specimens will be analyzed for amyloid beta, tau, and other related AD-associated neural markers and inflammatory cytokines. Cerebrospinal fluid specimens will be collected when the LP is performed before surgery (i.e. between the time of consent and anesthesia/surgery start), 24 hours after the start of anesthesia/surgery, and at the 6 week +/- 3 weeks follow up visit.

Cerebrospinal fluid and blood samples will be collected by a trained care provider under sterile

conditions. Blood and CSF samples will be stored at -80°C. All assay measurements will be performed at DUMC or in the accredited laboratory of a collaborator. All CSF and blood samples will be held in freezers in the Department of Anesthesiology and/or DUMC research facilities.

7.3.4 Specimen Shipment

Relevant specimens will be shipped on dry ice by FedEx overnight express to relevant collaborating labs for measurements, such as to MPI/Charles River and to the ADNI biomarker core lab at the University of Pennsylvania [or other appropriate laboratory](#) for tau, phospho-tau, and A[®] measurements.

7.4 Trial Schedule

7.4.1 Initial Consent and Visit

The following procedures and assessments will be conducted at the time of initial study consent or between the Initial study consent and the day of surgery:

Informed consent

Enrollment

Demographics (age, sex, and race)

Medical history

Neurocognitive testing will be done either in-person or remotely via teleconference (may include WTAR; HVLT-R; BVMT-R; WAIS-III —Digit Span, Digit Symbol Coding subtests, TrailTMT, Parts A & B, COWAT and Grooved Pegboard; MoCA) as well as the STOPBang assessment, VAS pain assessment, Falls assessments, Timed Up and Go Test, and Romberg Test

DASI

Psychological measures (including CES-D, STAI, SCL-90, SF-36)

Record concomitant medications administered per standard of care

Delirium Screening with the 3D-CAM instrument

Collect CSF sample/ LP prior to surgery (i.e. between the time of consent and the time of scheduled anesthesia/surgery start, which means it could be done at the initial visit or anytime between the time of consent at the initial visit and the time of scheduled anesthesia/surgery start on the day of surgery)

Collect research blood sample prior to surgery (i.e. between the time of consent and the time of scheduled anesthesia/surgery start, which means it could be done at the initial visit or anytime between the time of consent at the initial visit and the time of scheduled anesthesia/surgery start on the day of surgery)

LP vital signs will be collected and recorded by the study team before and after the LP if performed on outpatient basis (between

the time of consent and surgery day).

If the LP is performed while the patient is an inpatient (i.e. on the day of surgery), the study team will not collect and record vital signs, as these will already be obtained by the patient's clinical care team and recorded in the hospital electronic medical record for the patient, per standard of care.

-Randomization assignments will be made within 1 week prior to the patient's scheduled surgery.

7.4.2 Day 0 (Day of Surgery)

The following procedures and assessments will be conducted at this visit:

Collect CSF sample/ LP prior to surgery (if not done at the time of the Initial Consent and Visit)

Concomitant medications administered per standard of care.

Collect blood sample (if not done at the time of the Initial Consent and Visit)

Laboratory assessments

Study drug or placebo administration (within one hour prior to scheduled or actual surgery start time, and subsequent drug doses will be given every 6 hours thereafter until 3 days after surgery or hospital discharge, whichever comes first, up to a maximum of 13 doses) by the patient's clinical care team. Each case start time will be defined by the study team as either the start of the surgery/procedure or the start of anesthesia. If the case gets delayed by more than 6 hr and we've already given the first dose, we will give an additional dose prior to surgery, but under no conditions will the patient be given more than 13 doses total of CN-105.

EEG (within 2 hours before surgery as well as during and just aftersurgery). In the event that sufficient personnel or equipment are unavailable, or in the event that two MARBLE patients are having surgery at the same time, or in the event that there is insufficient time to place the EEG sensor on that patient's head before the start of surgery, the study team may not record EEG from all patients or at all points before, during, and just after surgery/anesthesia. Auditory tones will be played and auditory event-related potentials will be recorded if the pre-op and surgical workflow allows and if study personnel are available.

Vital signs (including heart rate) will be obtained and entered into the anesthetic record during the surgery by the clinical care team as per GCP, standard of care, and the American Society of Anesthesiology guidelines .

Continuous heart rate monitoring will be obtained for up to 15 minutes prior to surgery and during the surgery, to assess heart rate variability (R-R interval) as an index of vagal nerve function.

Grade II or higher AEs (and all SAEs) will be monitored and recorded from just after the first study drug or placebo administration until the end of the 6 week +/- 3 weeks postoperative study follow up visit.

Delirium Screening may be administered with 3D-CAM or CAM-ICU up to two times after surgery.

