Summary:	
Participants age 60 and over who are scheduled to undergo non-cardiac, non-neurologic surgical procedures that will take more than 2 hours, and who will be admitted to the hospital after surgery, will be prospectively approached for enrollment in this trial. Participants will undergo preoperative cognitive testing and will be randomized to receive either the apolipoprotein E (apoE) mimetic peptide CN-105 or placebo. Three sequential cohorts of 67 patients will be randomized to receive CN-105 vs placebo; the CN-105 patients in each successive cohort will receive a higher/escalated dose of CN-105. Thus, we will enroll at least 201 participants to reach the target of 150 participants who complete the trial.
 
Trial participants will undergo cognitive testing and complete quality-of-life (QOL) assessments before surgery and again 6 weeks +/- 3 weeks after surgery. These participants will receive either 1 of 3 dose levels of CN-105 or placebo, within one hour prior to case start time and continuing every 6 hours until postoperative day 3 or hospital discharge (whichever occurs first). We will also record noninvasive scalp electroencephalogram (EEG) data from these participants immediately before, during and after surgery. Cerebrospinal fluid (CSF) (up to 20 ml) and blood samples (up to 10 mL) will be collected prior to surgery (between the time of consent and the time the surgery will start), 24 +/- 2 hr after the scheduled surgery start/anesthesia induction and 6 weeks +/- 3 weeks after the scheduled surgery start/anesthesia induction. Cerebrospinal fluid samples will be assayed for amyloid beta, tau, and other Alzheimer's disease (AD)-associated markers, as well as inflammatory cytokines and markers; blood samples will be assayed for serum inflammatory markers and used for APOE genotyping studies. CN-105 levels will also be measured in both CSF and peripheral blood samples. Trial participants will return to the hospital 6 weeks +/- 3 weeks later to undergo repeat cognitive testing and CSF/blood draws.

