Consent, enrollment, randomization to CN-105 vs placebo, and preoperative cognitive testing.

Collect blood and cerebrospinal fluid samples between the time of consent and anesthesia/surgery start (preoperative sample), and 24 +/- 2 hr after anesthesia/surgery start; conduct delirium screening on each perioperative day that the participant remains in the hospital. Participants will receive either CN-105 or placebo at 6 hr intervals (for up to 13 consecutive doses) from within one hour prior to case start time until postoperative day 3 or hospital discharge, whichever comes first.

Participants will repeat cognitive testing and return for repeat lumbar puncture and blood draw 6 weeks +/- 3 weeks after surgery.

Intraoperative course variables from anesthesia record, EEG setup, and physiologic monitors will be obtained after the completion of the surgery.

Run biomarker and genotyping assays after CSF and blood samples obtained, analyze electroencephalographic and other data.

Study is complete after all assays run and all data analyzed

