7.4.6 Schedule of Events

Table 2: Schedule of Study Events for Trial

	Screening/ Baseline Study Visit	Within 1 week before surgery	Day 0 Surgery	Day 1 ^a Hospitalization	Days 2-4 Hospitalization	6 weeks (+/- 21 days) Follow- up
Informed consent	X					
Enrollment	X					
Randomization		X				
Demographics (age, sex, and race)	X					
Vital signs			X b, e	X b		X b
Medical history	X					
Neurocognitive testing ^c	X					X
Continuous Heart Rate Recording			X			
Laboratory assessments (additional routine clinical pre- + post-op labs will also be recorded)			X	X		X
Duke Activity Status Index	X					X
Psychological/physical measures ^d	X					X
Short Form-36	X					X
Lumbar puncture, Collect CSF samples			X ^e	X		X
Concomitant medications	X		X	X	X	X
Collect blood sample			X ^f	X		X
Drug administration ^g			X	X	X	
Electroencephalogram (EEG)			X ^h			
Grade II or higher AEs/ all serious AEs			X	X	X	X
3D-CAM or CAM-ICU for delirium screening	X		X	X	X ⁱ	X
Biomarker assays			X	X		X
Genotyping assays			X ^f			
Inflammatory protein analysis			X	X		X
CSF protein analysis			X	X		X

AE, adverse event; CSF, cerebrospinal fluid;
QOL, quality of life

^a 24 (+/- 2) hours post-surgery.

^b LP vital signs will be collected and recorded by the study team before and after the LP only if it is performed on an outpatient basis.

^c May include Hopkins Verbal Learning Test-Revised; BVMT-R ; Wechsler Adult Intelligence Scale-III—Digit Span, Digit Symbol subtests; Wechsler Test of Adult Reading; Trail Making Test Parts A & B; Grooved Pegboard; Montreal Cognitive Assessment (MoCA); STOPBang Questionnaire; visual analog scale pain assessment;

^d May include Center for Epidemiological Studies-Depression, State Trait Anxiety Inventory, Hopkins Symptom Checklist, Falls assessments, Timed Up and Go, and Romberg Assessments.

^e Between the time of consent and the scheduled anesthesia/surgery start time on the day of surgery.

^f Between the time of consent and the scheduled anesthesia/surgery start time on the day of surgery.

^g w/in 1 hr before the scheduled or actual start time of surgery and continuing every 6 hours through postoperative day 3 (up to 13 doses maximum) or hospital discharge, whichever occurs first

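### The pre-operative CSF and research blood windows close at surgery start, not at the first dose, so a baseline drawn up to about 60 minutes after dosing complies with the protocol

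*Combined protocol and SAP*

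**What the plan says.** **Sampling window.** For the day of surgery, section 7.4.2 lists "Collect CSF sample/ LP prior to surgery (if not done at the time of the Initial Consent and Visit"; the matching line for research blood states no time limit. Section 7.4.1 allows either sample "anytime between the time of consent at the initial visit and the time of scheduled anesthesia/surgery start on the day of surgery". Table 2 notes e and f (7.4.6) give "Between the time of consent and the scheduled anesthesia/surgery start time on the day of surgery". Section 7.1.1 has "An LP will be performed prior to surgery (between the time of consent and the time of scheduled anesthesia/surgery start". Section 7.3.3 places the blood draw "sometime between the patient being consented and scheduled anesthesia/surgery start time" and the CSF draw before the start, without the word scheduled. The Protocol Summary has "between the time of consent and the time the surgery will start", the Schematic has "between the time of consent and anesthesia/surgery start (preoperative sample", and section 4.1 closes the window at the scheduled start.

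**First dose.** Section 7.4.2 has "Study drug or placebo administration (within one hour prior to scheduled or actual surgery start time". Sections 4.1, 6.2 and 10.3.1 and Table 2 note g give the same hour. Case start may be taken as the start of anesthesia or of surgery (4.1, 7.4.2).

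**What must precede the dose.** Section 7.3.1 requires the metabolic panel and blood count to be taken before the first dose. Section 7.3.2 plans no pre-operative CN-105 assay, on the ground that no drug should be present before dosing begins. Neither section sets that rule for the CSF or research blood.

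**Use of the baseline.** The pre-operative CSF is the reference for secondary endpoint 1, the change in four cytokines to 24 hours and to 6 weeks (4.2.2, 10.1.3). It also serves the exploratory CSF Alzheimer's markers. Blood drawn at the same time points is assayed for serum inflammatory markers (4.1).

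**The concern.** The dosing window opens before the sampling window closes, so a sample labelled pre-operative can be post-dose without any deviation. A change score needs a reference value that treatment has not touched. Saline cannot move a baseline drawn after the infusion, but CN-105 might, since section 5.4.2 describes it as modulating the inflammatory response. Any error would therefore fall on one arm only, and randomization would not balance it. For blood the route is direct, because the drug is given intravenously. For CSF it is uncertain, because the extent of entry into human CSF is one of the things the trial sets out to measure (7.3.2).

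Nor would the planned assays reveal the problem, because no pre-operative CN-105 level is measured. Only the recorded times could show it.

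The overlap can occur in practice. Lumbar puncture on the day of surgery is expressly foreseen (7.1.1, 7.4.2) and includes a wait of about 10 minutes after the numbing spray. It shares the pre-operative period with EEG set-up, which the protocol concedes may be dropped for lack of time or staff. The clinical care team gives the dose, and nothing tells it to wait for the draw.

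**Working it through.** The plan states no figure here to reproduce. The check is window arithmetic, followed by the direction of any error.

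**1. Longest compliant gap.** Gap = latest permitted draw minus earliest permitted start of the first dose. Time 0 is the start used as anchor, so the earliest dose is at −60 min (7.4.2).

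| Reading of the text | Formula | Result (min) |
|---|---|---|
| Dose and draw tied to the same start | 0 − (−60) | 60 |
| Draw closes at scheduled start; dose timed to an actual start L min later | max(0, 60 − L) | 45, 30, 15, 0 for L = 15, 30, 45, 60 |
| Dose timed to scheduled start; draw closes at actual start after a delay of D min | 60 + D | 120, 180, 420 for D = 60, 120, 360 |
| Dose timed to anesthesia start; draw closes at surgery start A min later | 60 + A | 75, 90, 105 for A = 15, 30, 45 |

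L, D and A are assumed values; the documents give none. The third row rests on the windows that omit the word scheduled (Protocol Summary, Schematic, 7.3.3 for CSF, 7.4.2). The fourth rests on the choice of case start in 4.1 and 7.4.2, with the draw limited only by surgery start as in the Protocol Summary. It needs no delay.

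**2. How much of the dose could be in.** In the 60-minute case, the time from end of infusion to draw is 60 minus the infusion time.
- Section 6.2.1 (5 to 10 min, at most 30): 60 − 5 = 55, 60 − 10 = 50, 60 − 30 = 30 min.
- Section 10.3.1 (15 to 30 min): 60 − 15 = 45, 60 − 30 = 30 min.

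The two sections differ on infusion time, but under either the whole first dose can be in at least 30 minutes before the latest compliant draw.

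**3. Direction.** Let q be the share of CN-105 baselines drawn after dosing, and b the mean amount by which that dose has lowered the marker at the draw.
- Computed mean change, CN-105 = true change + q × b.
- Computed mean change, placebo = true change.
- Shift in the arm difference = q × b.

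If b is positive, the CN-105 rise looks larger than it was and apparent benefit shrinks. If b is zero, nothing shifts. Neither q nor b is in the documents, and the planned test is rank-based, so this gives direction and not size. It applies to a rise, which is how 4.2.2 words all four cytokines. Section 10.1.3 words its power statements for IL-8 and MCP-1 as smaller decreases. If that is meant, the same upward shift would count toward the sought effect for those two.

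**4. Reach.** Adverse events are counted after the first dose. Delirium is scored by bedside instruments, and cognition by tests taken before and after surgery. None uses the CSF or research blood baseline.

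**The case against.** The strongest reply is that the intent is already clear. Section 7.3.2 makes sense only if the pre-operative sample is pre-dose, and the Day 0 list places CSF and blood above study drug. On this view the protocol lacks a clarifying clause and nothing more. Moreover, no harm is shown. Sixty minutes needs the earliest permitted dose and the last permitted draw, samples taken at an earlier visit are safe, and a draw before incision precedes the surgical insult whose effect the endpoint measures. If an early dose did lower cytokines, the error in a rise would work against the drug.

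Much of this stands. The intent is evident, 60 minutes is a boundary value, and the effect may be zero. Two parts do not stand. List order is not a rule: the Day 1 list uses the same order once dosing is under way, and the Day 0 list puts EEG, which may begin two hours before surgery, below a dose due within one hour. Evident intent also does not make a post-dose draw a deviation. The authors wrote the needed condition for the clinical labs and left it off the research samples.

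A reader might infer that the team chose a post-dose baseline, or that baselines were in fact drawn after dosing. The documents support neither. Section 7.3.2 points the other way on intent, and nothing reports the order of draws and doses.

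**Conclusion.** The gap is real and narrow. As written, a Day 0 CSF or research blood baseline may follow the first dose by up to about 60 minutes, and by more under the delay or mixed-anchor readings. Any resulting error is confined to the CN-105 arm. It touches secondary endpoint 1 and the exploratory CSF and serum biomarkers. Its size cannot be derived and may be zero; on the drug's hypothesized action it would dilute apparent benefit wherever the measured change is a rise.

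A reader might go further and conclude that the cytokine result is invalid or tilted toward CN-105, or that the safety conclusion is at risk. The documents do not support this. They give no share of post-dose baselines and no early effect on CSF or serum, and the adverse event, delirium and cognitive comparisons do not use these samples.

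The verdict rests on the protocol text alone. Section 6.3 mentions a manual of operational procedures, which is not among the documents and may already require sampling before dosing. Priority: minor to moderate, because the effect is unquantified but the remedy costs almost nothing.

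**What to change.** Add *and before the first dose of study drug* to every pre-operative CSF and research blood window: Protocol Summary, Schematic, 4.1, 7.1.1, 7.3.3, 7.4.1, 7.4.2 and Table 2 notes e and f. Changing only some of them would leave the protocol in conflict with itself. Record the draw time. The longest compliant gap then falls from 60 minutes to zero, and no sample size, power or alpha figure changes.

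For patients already treated, compare draw times with dose times. Dose times are recorded (6.3). A form is completed at each draw (14.1), but 14.1 does not say that it carries the time, so the look-back works only where it does. Then repeat the cytokine comparison as a sensitivity analysis that excludes, in both arms, patients whose baseline followed the first dose. The order of draw and dose is set by staff blind to arm (10.3.2), so the exclusion does not select by treatment.

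The cost is one clause in eight places, a time field if the form lacks one, and some precision in the sensitivity analysis. If a share x is dropped from each arm, the standard error grows by about 1/√(1 − x): 1.03, 1.05 and 1.12 for assumed x of 5%, 10% and 20%. The planned 39 placebo patients would become about 37, 35 and 31, and the 117 on CN-105 about 111, 105 and 94. The placebo group, being the smaller, sets most of that precision.
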